6.3 Concomitant medications

Patients must be instructed not to take any medications (over-the-counter or other products) during the protocol treatment period without prior consultation with the investigator. The investigator should instruct the patient to notify the study site about any new medications he/she takes after the start of study drug. All medications (other than study drug) and significant non-drug therapies (including physical therapy and blood transfusions) taken within 28 days of starting study treatment through the 30-day safety follow up visit should be reported on the CRF.

6.3.1 Permitted concomitant therapy

Cytochrome P450 and P-glycoprotein inhibitors/inducers/substrates

Co-administration with strong inhibitors of CYP3A4 or PgP should be avoided; and may cause increased everolimus concentrations. For a current table of Substrates, Inhibitors and Inducers please access the following website:

<http://www.fda.gov/Drugs/DevelopmentApprovalProcess/DevelopmentResources/DrugInteractionsLabeling/ucm093664.htm>

Everolimus is metabolized by CYP3A4 in the liver and to some extent in the intestinal wall. Therefore, the following are recommended:

- Co-administration with strong inhibitors of CYP3A4 (e.g., ketoconazole, itraconazole, ritonavir) or P-glycoprotein (PgP) inhibitor should be avoided.
- Co-administration with moderate CYP3A4 inhibitors (e.g., erythromycin, fluconazole) or PgP inhibitors should be used with caution. If a patient requires co-administration of moderate CYP3A4 inhibitors or PgP inhibitors, reduce the dose of everolimus by approximately 50%. Additional dose reductions to every other day may be required to manage toxicities. If the inhibitor is discontinued, the Everolimus dose should be returned to the dose used prior to initiation of the moderate CYP3A4/PgP inhibitor after a washout period of 2 to 3 days.
 - **TSC with SEGA:** Everolimus trough concentrations should be assessed approximately 2 weeks after the addition of a moderate CYP3A4/PgP inhibitor. If the inhibitor is discontinued the Afinitor dose should be returned to the dose used prior to initiation of the inhibitor and the everolimus trough concentration should be re-assessed approximately 2 weeks later.
- Grapefruit, Seville oranges, and starfruit affect P450 and PgP activity. Concomitant use should be avoided.
- If patients require co-administration of a strong CYP3A4 inducer, consider doubling the daily dose of Afinitor (based on pharmacokinetic data), using increments of 5 mg or less. This dose of Afinitor is predicted to adjust the AUC to the range observed without inducers. However, there are no clinical data with this dose adjustment in patients.

receiving strong CYP3A4 inducers. If the strong inducer is discontinued, consider a washout period of at least 3 to 5 days (reasonable time for significant enzyme de-induction), before the Afinitor dose is returned to the dose used prior to initiation of the strong CYP3A4 inducer.

- **TSC with SEGA** Patients receiving concomitant strong CYP3A4 inducers (e.g., the enzyme inducing antiepileptic drugs carbamazepine, phenobarbital, and phenytoin) may require an increased Afinitor dose to attain trough concentrations of 3 to 15 ng/mL. Double the daily dose of Afinitor and assess tolerability. Assess the everolimus trough level two weeks after doubling the dose. Further adjust the dose if necessary to maintain the trough within the 3 to 15 ng/mL range. If the strong inducer is discontinued, the Afinitor dose should be returned to the dose used prior to initiation of the strong CYP3A4 inducer and the everolimus trough concentrations should be assessed approximately 2 weeks later.
- This dose adjustment of Everolimus is intended to achieve similar AUC to the range observed without inducers. However, there are no clinical data with this dose adjustment in patients receiving strong CYP3A4 inducers. If the strong inducer is discontinued the Everolimus dose should be returned to the dose used prior to initiation of the strong CYP3A4/PgP inducer.

Please refer to Table 6-8 listing relevant inducers and inhibitors of CYP3A and Table 6-9 for a list of relevant substrates, inducers, and inhibitors of PgP.

Everolimus and drugs influencing CYP3A4 enzyme

Everolimus is a substrate of CYP3A4, and a substrate and moderate inhibitor of the multidrug efflux pump, PgP (PgP, MDR1, and ABCB1). Therefore, extent of absorption and subsequent elimination of systemically absorbed everolimus may be influenced by products that are substrates, inhibitors, or inducers of CYP3A4 and/or PgP. Concurrent treatment with strong CYP3A4-inhibitors should be avoided. Refer to Table 6-2 in section 6 for a comprehensive list of inducers and inhibitors of CYP3A4 and Table 6-3]for a list of relevant substrates, inducers and inhibitors of PgP. Inhibitors of PgP may decrease the efflux of everolimus from brain or tumor and therefore increase everolimus concentrations in these tissues. In vitro studies showed that everolimus is a competitive inhibitor of CYP3A4 and of CYP2D6, potentially increasing the concentrations of products eliminated by these enzymes. Thus, caution should be exercised when co-administering everolimus with CYP3A4 and CYP2D6 substrates with a narrow therapeutic index. Clinical studies have been conducted in healthy subjects to assess pharmacokinetic drug interactions between everolimus and potential CYP3A modifiers (ketoconazole, verapamil, erythromycin, rifampin, midazolam, and HMGCoA reductase inhibitors (statins).

Table 6-7 Clinically relevant drug interactions: inducers, and inhibitors of isoenzyme CYP3A

Inducers
Strong inducers: avasimibe, carbamazepine, enzalutamide, mitotane, phenobarbital, phenytoin, rifabutin, rifampin (rifampicin), St. John's wort (hypericum perforatum)
Moderate inducers: bosentan, efavirenz, etravirine, genistein, lersivirine, lopinavir, modafinil, naftilin, ritonavir, semagacestat, [talviraline], thioridazine, tipranavir

Weak inducers:

amprenavir, aprepitant, armodafinil (R-modafinil), bexarotene, boceprevir, brivacetam, clobazam, danshen, dexamethasone, Echinacea, eslicarbazepine, garlic (allium sativum), ginseng, gingko (ginkgo biloba), glycyrrhizin, methylprednisolone, nevirapine, oxcarbazepine, pioglitazone, prednisone, [pleconaril], primidone, quercetin, raltegravir, ritonavir, rufinamide, sorafenib, stribild (combo of elvitegravir, cobicistat, emtricitabine, and tenofovir), sulfapyrazone, telaprevir, terbinafine, ticagrelor, ticlopidine, topiramate, [troglitazone], vemurafenib, vicriviroc/ritonavir vinblastine

Inhibitors**Strong inhibitors:**

boceprevir, clarithromycin, cobicistat, conivaptan, danoprevir / ritonavir, eltegravir/ritonavir, grapefruit juice, indinavir, indinavir/ritonavir, itraconazole, ketoconazole, lopinavir/ritonavir, mibepradil, nefazodone, neflifinavir, posaconazole, ritonavir, saquinavir, saquinavir/ritonavir, telaprevir, telithromycin, tipranavir/ritonavir, troleandomycin, voriconazole

Moderate inhibitors:

Amprenavir, aprepitant, atazanavir, atazanavir/ritonavir casopitant, cimetidine, ciprofloxacin, crizotinib, cyclosporine, darunavir, darunavir/ritonavir, diltiazem, dronedarone, erythromycin, fluconazole, fosamprenavir, grapefruit juice (citrus parasida fruit juice), imatinib, lomitapide, netupitant, nilotinib, schisandra sphenanthera, tofisopam, verapamil

Weak inhibitors:

almorexant, alprazolam, alprazolam, amiodarone, amlodipine, amlodipine, atorvastatin, azithromycin, berberine, bicalutamide, bicalutamide, blueberry juice, cilostazol, cilostazol, cimetidine, clotrimazole, clozoxazole, cranberry juice, cyclosporine, delavirdine, everolimus, fluoxetine, fluvoxamine, fosapreptitant, ginkgo, goldenseal, isoniazid, isoniazid, ivacaftor, lopinavir, linagliptin, nilotinib, oral contraceptives, pazopanib, peppermint oil, propiverine, ranitidine, ranitidine, ranolaxine, ranolazine, resveratrol, roxithromycin, Seville orange, simeprevir, sitaxentan, tabimorelin, tacrolimus, teriflunomide, ticagrelor, tipranavir/ritonavir, tolvaptan, zileuton

Table 6-8 Clinically relevant drug interactions: substrates, inducers, inhibitors of PgP and PgP/CYP3A dual inhibitors

Substrates
afatinib, alfuzosin, aliskiren, alogliptin, ambrisentan, apixaban, apremilast, aprepitant, atorvastatin acid, atorvastatin, azithromycin, boceprevir, bosentan, carvedilol, caspofungin, ceritinib, cerivastatin, citalopram, colchicine, CP-481,715, cyclosporine, dabigatran, digoxin, docetaxel, domperidone, doxepin, doxorubicin, eribulin, everolimus, fentanyl, fexofenadine, fidaxomicin, fluvastatin, fosamprenavir, gatifloxacin, idelalisib, iloperidone, indacaterol, indinavir, irbesartan, lacosamide, lapatinib, levetiracetam, levofloxacin, linagliptin, linezolid, loperamide, losartan, maraviroc, mirabegron, moxifloxacin, naloxegol, nateglinide, nevirapine, nintedanib, Iodaterol, paclitaxel, pantoprazole, paroxetine, pazopanib, phenytoin, posaconazole, pravastatin, proguanil, quinidine, quinine, ranolazine, riociguat, risperidone, ritonavir, rivaroxaban, saquinavir, silodosin, simeprevir, simvastatin, sirolimus, sitagliptin, sofosbuvir, sorafenib, tacrolimus, talinolol, telaprevir, tenofovir, ticagrelor, tipranavir, tolvaptan, topotecan, umeclidinium, valsartan, vardenafil, vincristine, voclosporin, voriconazoleeverolimus
Inducers
avasimibe, carbamazepine, efavirenz, genistein, phenytoin, quercetin, rifampin, St John's wort
PgP Inhibitors and PgP/CYP3A Dual Inhibitors
PgP Inhibitors alogliptin, canagliflozin, cremophor RH40, curcumin, ketoconazole, lapatinib, lopinavir/ritonavir, mirabegron, propafenone, simeprevir, valsopdar, vandetanib, voclosporin
PgP/CYP3A Dual Inhibitors amiodarone, azithromycin, captopril, carvedilol, clarithromycin, conivaptan, diltiazem, dronedarone, elacridar, erythromycin, felodipine, fluvoxamine, ginkgo (ginkgo biloba), indinavir, indinavir/ritonavir, itraconazole, mibepradil, milk thistle (silybum marianum), nelfinavir, nifedipine, nitrendipine, paroxetine, quercetin, quinidine, ranolazine, rifampin, ritonavir, saquinavir/ritonavir, Schisandra chinensis, St John's wort (hypericum perforatum), talinolol, Telaprevir, telmisartan, ticagrelor, tipranavir/ritonavir, tolvaptan, verapamil
Reference: Internal Clinical Pharmacology Drug-drug interaction (DDI) memo, updated Oct. 2, 2011,29-Oct-2012 which summarizes DDI data from three sources including the FDA's "Guidance for Industry, Drug Interaction Studies", the University of Washington's Drug Interaction Database, and Indiana University School of Medicine's Drug Interaction Table.

Vaccinations

Immunosuppressants may affect the response to vaccination and vaccination during treatment with Everolimus may therefore be less effective. The use of live vaccines should be avoided during treatment with Everolimus. For pediatric patients with SEGA that do not require immediate treatment, complete the recommended childhood series of live virus vaccinations prior to the start of therapy according to local treatment guidelines. Examples of live vaccines are: intranasal influenza, measles, mumps, rubella, oral polio, BCG, yellow fever, varicella, and TY21a typhoid vaccines.

7 Visit schedule and assessments

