6.2.1.2 Dosing modifications

For patients who do not tolerate the protocol-specified dosing schedule, dose adjustments are not permitted.

Table 6-1 and Table 6-2 list the dosing guidelines for Everolimus-related non-hematologic and hematologic toxicities.

Management of severe or intolerable adverse drug reactions (ADRs) may require temporary dose interruption of Afinitor therapy.

The proceeding sections summarize recommendations for dose interruption, or discontinuation of Afinitor in the management of ADRs. General management recommendations are also provided as applicable. Clinical judgment of the treating physician should guide the management plan of each patient based on individual benefit/risk assessment.

Table 6-1 Dosing guidelines for Everolimus-related non-hematologic toxicities

Toxicity	Action
Non-Infectious Pneumonitis	Discontinue Everolimus.
Reactivation of HBV or HCV flare	Discontinue Everolimus.
AST or ALT elevation Grade 1 ($>$ ULN - 3.0 x ULN)	Maintain current dose level
Grade 2 ($>$ 3.0 - 5.0 x ULN)	
AST or ALT elevation Grade 3 ($>$ 5.0 - 20.0 ULN)*	Discontinue Everolimus
AST or ALT elevation Grade 4 ($>$ 20 x ULN)*	Discontinue Everolimus
Intolerable grade 2 mucositis, or grade 3 AE, except hyperglycemia or hypertriglyceridemia or hypercholesterolemia (see Section 6.2.3.8)	Discontinue Everolimus
Any other grade 4	Discontinue Everolimus
Grade 3 or 4 clinical liver failure (asterixis or encephalopathy/coma)	Discontinue Everolimus

* Should HCV flare be confirmed, the guidelines for flare must take precedence (Table 6-6)

Table 6-2 Dosing guidelines for Everolimus-related hematologic toxicities

Toxicity	Action
Grade 2 thrombocytopenia (platelets $<$ 75, \geq 50 x10 ⁹ /L)	No action
Grade 3 thrombocytopenia (platelets $<$ 50, \geq 25 x10 ⁹ /L)	Discontinue Everolimus
Grade 4 thrombocytopenia (platelets $<$ 25 x10 ⁹ /L)	Discontinue Everolimus
Grade 3 neutropenia or anemia (neutrophil $<$ 1, \geq 0.5 x10 ⁹ /L)	Discontinue Everolimus
Grade 4 neutropenia or anemia	Discontinue Everolimus
Febrile neutropenia	Discontinue Everolimus

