7.1 Study flow and visit schedule

Table 7-1 Visit evaluation schedule

	Screening / Baseline	RT Day 22	RT Day 43	Post RT day 15	Post RT day 22	Post RT week 6	Post RT week 14	Post RT week 26
Visit no.	1	2	3	4	5	6	7	8
Treatment days*	-21 to -1							
Demography/informed consent (D)	X							
Inclusion/exclusion criteria (D)	X							
Relevant medical history/current medical conditions (D)	X							
Diagnosis and extent of cancer (D)	X							
Prior/post antineoplastic therapy (D)	X							
HIV history (S)	X							
Vital signs (D)	X	X	X	X	X	X	X	X
Height (D)	X							
Weight (D)	X	X	X	X	X	X	X	X
Physical examination (S)	X	X	X	X	X	X	X	X
ECOG performance status (D)	X	X			X	X	X	X
EKG ¹ (D)			X					
Correlative studies	X	X	X	X	X	X	X	X
Hematology ² (D)	X		X	X	X			
Coagulation (D)	X		X	X	X			
Biochemistry ³ (D)	X		X	X	X			
Serum Lipid Profile ⁴ (D)	X		X	X	X			
Prior/concomitant medications (D)	X			X	X			

	Screening / Baseline	RT Day 22	RT Day 43	Post RT day 15	Post RT day 22	Post RT week 6	Post RT week 14	Post RT week 26
Visit no.	1	2	3	4	5	6	7	8
Treatment days*	-21 to -1							
Everolimus ⁵				X				
HBV-DNA, HBsAg, HBs Ab, HBc Ab, HCV-RNA-PCR ⁶ (D)	X							
HBV DNA, HCV RNA-PCR ⁷ (D)	X							

* (+/- 1 day for visits 2,3,4,5; +/- 1 week for visits 6,7,8)

1. Baseline ECG is a standard 12 lead and must be performed within 21 days of first dose for patients enrolled and may be repeated at the investigator's discretion if clinically indicated
2. Hematology tests include a complete blood count (CBC). A total white blood cell (WBC) with absolute differentials (including neutrophil count plus bands, lymphocyte, monocyte, eosinophil, basophil counts), red blood cells (RBC), hemoglobin (Hgb), and a platelet count.
3. Serum Chemistry must include: BUN or uric acid, creatinine, LDH, total protein, electrolytes (sodium, potassium and calcium), total bilirubin, GGT, albumin, alkaline phosphatase, AST/sGOT fasting glucose.
4. Serum fasting lipid profile must include: total cholesterol and triglycerides. Patients should be in fasting state.
5. Everolimus is taken once daily for a total of five days, with drug dispensed at Visit 4.

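### Section 6.3.1 lets sites consider doubling everolimus with a strong CYP3A4 inducer, with no maximum tied to the cohort dose

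*Protocol*

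**What the plan says.** Section 6.3.1 of the Protocol covers co-administration with drugs that affect CYP3A4. For a patient who requires a strong inducer, sites are told to "consider doubling the daily dose of Afinitor (based on pharmacokinetic data), using increments of 5 mg or less". The reason given is pharmacokinetic: "This dose of Afinitor is predicted to adjust the AUC to the range observed without inducers". The next sentence adds a caution: "However, there are no clinical data with this dose adjustment in patients". A later bullet repeats the aim: "This dose adjustment of Everolimus is intended to achieve similar AUC to the range observed without inducers".

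The design in sections 4.1, 6.1 and 9.1 has two dose levels. The first three patients receive 5 mg daily. The 10 mg level opens only if the 5 mg cohort passes. With two DLTs, 10 mg is not attempted and the 5 mg cohort is expanded to 10 patients. On course length, note 5 to Table 7-1 states: "Everolimus is taken once daily for a total of five days, with drug dispensed at Visit 4".

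On toxicity, the moderate-inhibitor bullet of section 6.3.1 says: "Additional dose reductions to every other day may be required to manage toxicities". Section 6.2.1.2 says: "For patients who do not tolerate the protocol-specified dosing schedule, dose adjustments are not permitted".

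**The concern.** The wording of section 6.3.1 reads as label text for long-term use: it contains separate instructions for TSC with SEGA and trough targets that have no role here. Moved into a five-day, two-level dose-finding course, it gives sites a route to a daily dose above the level under test. The escalation rule exists so that nobody receives 10 mg until 5 mg has been found tolerable, and nobody receives more than 10 mg at all. An instruction elsewhere in the protocol that permits either dose weakens that safeguard.

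Two things are at stake. One is the safety of the individual patient, if the doubled dose overshoots. The other is the reading of the dose levels, because a patient counted in the 5 mg cohort may have taken 10 mg, with no measurement to show whether exposure was that of 5 mg.

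**Working it through.** **1. Nominal doses.** Inputs: cohort doses of 5 and 10 mg (section 4.1), the factor of two and the 5 mg step (section 6.3.1), and five daily doses (Table 7-1, note 5). The protocol gives no maximum dose and no size for the fall in AUC under an inducer, so it has no figure of its own to reproduce on this point.

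- 5 mg cohort: 2 × 5 = 10 mg daily, the level still closed or already barred. Course total if doubled from day 1: 5 × 10 = 50 mg, against 5 × 5 = 25 mg planned.
- 10 mg cohort: 2 × 10 = 20 mg daily, twice the highest planned level. Course total if doubled from day 1: 5 × 20 = 100 mg, against 5 × 10 = 50 mg planned.
- If the increments mean one step per day from the cohort dose, the totals are lower: 5 + 10 + 10 + 10 + 10 = 45 mg and 10 + 15 + 20 + 20 + 20 = 85 mg. The daily dose reached is the same.

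**2. Does anything else in the protocol stop this?**

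- Section 5.1: no exclusion criterion names strong inducers. Section 6.3.1 says strong inhibitors should be avoided, but has no matching rule for inducers.
- Section 6.2.1.2 bars adjustment only for patients who do not tolerate the schedule.
- Section 6.3 requires the investigator to be consulted before any medication is taken, but the guidance the investigator then finds is section 6.3.1.
- Section 6.1 requires dose changes to be recorded, and section 11.2 sets weekly calls that cover cohort management. These document a dose; they do not cap it.
- Section 10 lists dose increases among amendments that need IRB approval. That governs changes to the protocol, not a dose the protocol already allows.

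**3. Could exposure be checked?** Table 7-1 schedules no everolimus level at any visit. The safety bloods after dosing are at post-RT day 22. If the first dose is taken on post-RT day 15, the last is on day 15 + 4 = 19, so these bloods come after the course has ended.

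**4. What might doubling do to exposure?** Let f be the fractional fall in AUC caused by the inducer. This is an assumption. Relative to the AUC without an inducer, the undoubled dose gives 1 − f and the doubled dose gives 2(1 − f).

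| Assumed f | Cohort dose, not doubled | Doubled dose |
|---|---|---|
| 0.25 | 0.75 | 1.5 |
| 0.40 | 0.60 | 1.2 |
| 0.50 | 0.50 | 1.0 |
| 0.60 | 0.40 | 0.8 |
| 0.70 | 0.30 | 0.6 |

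Doubling matches exposure exactly only at f = 0.50. If induction has gone (f = 0), the doubled dose gives 2.0. That case matters because section 6.3.1 suggests waiting at least 3 to 5 days after the inducer stops before the dose is brought back down, and this can take up the rest of a five-day course.

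**5. Who could be affected?** The strong inducers are listed in Table 6-7. Enzalutamide and mitotane would largely be caught by exclusion 1 (recent anticancer therapy) or 9 (another malignancy). Rifampin or rifabutin given for an active infection would largely be caught by exclusion 5c. St John's wort needs consultation under section 6.3 and can hardly be called required. Apart from avasimibe, that leaves carbamazepine, phenobarbital and phenytoin, which section 6.3.1 itself calls enzyme-inducing antiepileptics.

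**6. The alternate-day wording.** Section 6.3.1 foresees reducing to alternate days to manage toxicity. Section 6.2.1.2 permits no adjustment for a patient who does not tolerate the schedule. Both address the same situation and cannot both be followed.

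**The case against.** The strongest reply is that milligrams are not exposure. Doubling is meant to restore the AUC seen without an inducer, so a patient on 10 mg plus an inducer may be a fair representative of the 5 mg level. Leaving the dose at 5 mg would not be neutral either: the table above shows under-exposure across the whole assumed range. This stands. It is why the remedy is to keep strong inducers away from the course, and not only to cap the dose. It does not rescue the instruction, because the protocol calls the match predicted, reports no clinical data, and has no means of checking it.

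It is also fair to say that the advice is discretionary, limited to twofold and confined to patients who require the inducer; that 10 mg is described as the full approved dose; and that Tables 6-1 and 6-2 provide for stopping on toxicity. All of this limits the size of the problem.

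A reader might infer several stronger things that the documents do not support:

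- **That the escalation decision is biased.** The size and direction of any mismatch are unknown, and there is no effect if AUC is matched.
- **That 20 mg is an untested dose.** The protocol shows only that it is not a level of this trial.
- **That a trough check is planned but mistimed.** The instruction "Assess the everolimus trough level two weeks after doubling the dose" is written for TSC with SEGA and does not apply to this population.
- **That rifampin and St John's wort carry opposite dosing orders**, because Table 6-8 lists them as inducers and as dual inhibitors. That table is a compiled reference list, and other drugs are listed twice in the same way. Deciding which entry is wrong would need pharmacology from outside the documents.

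**Conclusion.** The point holds as a defect in a stated dosing instruction. Section 6.3.1 permits a nominal 10 mg in the 5 mg cohort before, or despite a bar on, escalation, and a nominal 20 mg in the 10 mg cohort. No other provision sets a ceiling, and nothing scheduled would show whether exposure was matched. The contradiction with section 6.2.1.2 over alternate-day dosing is plain but secondary.

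The size is minor to moderate. The protocol gives no frequency for strong-inducer use; the judgement that few patients are affected rests on the other exclusion criteria removing most of the listed drugs. How a patient on a changed dose counts for the DLT rule may be settled in an analysis plan not seen here, and is not part of this point.

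**What to change.** In section 6.3.1:

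- Delete the doubling advice in both bullets where it appears, the alternate-day reduction, and the TSC/SEGA text.
- State that no patient receives more than the assigned cohort dose.
- State that patients who require a strong CYP3A4 inducer do not receive everolimus unless the inducer can be avoided around the five-day course, with the sponsor setting the interval before the first dose.

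The halving rule for moderate inhibitors can stay as it is.

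The cost is a wording amendment. The downside is that an occasional patient on a strong inducer becomes ineligible or has to switch drugs. The cohort sizes and the escalation rule do not change.
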